### 5.10. Exploratory Analyses

If not indicated otherwise the analyses will be performed based on the respective MITTv5 population comparing HMTM 16 mg/day with control as described in Section 5.9.2.1, without any further sensitivity and supplementary analysis.

Descriptive analysis calculated by treatment group and visit based on the observed data will be given.

These analyses are broadly classified into two groups, analyses of clinical endpoints and imaging endpoints. Of particular interest are to test the hypotheses that HMTM 16mg/day leads to a reduction in MRI total lesion volume over time, that HMTM 16 mg/day increases the F-FDG-PET SUVR in cerebellum measured with respect to pons, and that HMTM 16 mg/day shows a significant reduction in decline on the composite endpoint in the mild (CDR 0.5) population.

Sponsor:	TauRx Therapeutics Ltd.		
Protocol:	TRx-237-039		
Document Version No.:	3.0	Document Date:	07-JUN-2023

#### 5.10.1. ADAS-cog13

The ADAS-cog13 is assessed at Baseline pre-dose, 13, 26, 39 and 52 weeks (or early termination) during the double-blind treatment phase and will be analyzed using the MMRM as described in Section 5.9.2.1.

This analysis will be repeated for the subgroup on subjects with MCI-AD, and mild AD (MMSE 20-27).

#### 5.10.2. Composite Scale

The Composite Scale is assessed at Baseline pre-dose, 13, 26, 39 and 52 weeks (or early termination) during the double-blind treatment phase and will be analyzed using the MMRM as described in Section 5.9.2.1, but also investigating the treatment effect at Week 39.

Additionally, this analysis will be repeated in subjects with CDR of 0.5 at Screening, and CDR of 1-2 at Screening.

#### 5.10.3. MMSE

The MMSE is assessed at Screening and Week 52 (or early termination) during the double-blind treatment phase and will be analyzed using the ANCOVA as described in Section 5.9.3.2 for the ITTv5 population.

#### 5.10.4. CDR-SOB

The CDR-SOB is assessed at Screening and Week 52 (or early termination) during the double-blind treatment phase and will be analyzed using the ANCOVA as described in Section 5.9.3.2 for the ITTv5 population.

#### 5.10.5. MRI Parameters

The atrophy of further brain MRI parameters (putamen, nucleus accumbens, and nucleus basalis) will be analyzed using the MMRM as described in Section 5.9.3.1.

Furthermore, the Baseline values of putamen, nucleus accumbens, and nucleus basalis will be included as covariates in the analysis of secondary endpoints whole brain, and temporoparietal lobe (see Sections 5.9.3.1 and 5.9.3.3).

In a sensitivity analysis of the two co-primary endpoints ADAS-cog11 and ADCS-ADL23, the Baseline values of MRI whole brain volume and MRI T1 imaging TLV and their interactions with treatment (the additive terms are included as well) will be added to the analysis model (see Section 5.9.2.1).

#### 5.10.6. F-FDG-PET Parameters

The F-FDG-PET SUVRs in subjects with mild AD (CDR of 0.5 at Screening):

- temporal lobe normalized to cerebellum,
- cerebellum normalized to pons,

Sponsor:	TauRx Therapeutics Ltd.		
Protocol:	TRx-237-039		
Document Version No.:	3.0	Document Date:	07-JUN-2023

- parietal lobe normalized to pons and normalized to cerebellum, and
- frontal lobe normalized to pons and normalized to cerebellum

will be analyzed using the ANCOVA as described in Section 5.9.3.2.

Other SUVR regions anterior, and posterior cingulate gyrus will be examined descriptively by summarizing the actual value and change from Baseline.

#### **5.10.7. MRI Hypointensities and Hyperintensities**

The TLV (hypointensities) based on MRI T1 imaging and the MRI hyperintensities total volume based on MRI FLAIR will be analyzed using the MMRM as described in Section 5.9.3.1. These parameters and the other MRI FLAIR sub-parameters deep volume, infratentorial volume, and periventricular volume will be listed together with the other MRI parameters.

#### **5.10.8. *ApoE* Genotype**

A subject data listing will be provided for *ApoE* genotype data, including only the subjects who consented to this determination. In this listing, the genotype classification (presence/absence of the ε4 allele) will be given, but not the detailed genotype.

The influence of the genotype (presence/absence of ε4 allele) will be evaluated for the two co-primary endpoints and selected secondary endpoints (MRI whole brain volume, and F-FDG-PET temporal lobe) by adding the genotype classification as a fixed factor into the MMRM and ANCOVA model (see Section 5.9.2.1).

#### **5.11. Statistical Parametric Mapping Analyses (SPM)**

This section describes the planned SPM analyses, performed by an external vendor. Changes to these analyses, will be discussed and presented in the CSR or SPM analysis report. Further analyses might be performed dependent on the outcome of these exploratory analyses.

SPM12 is used to process volumetric MRI (vMRI), Arterial Spin Labeling (ASL) MRI and F-FDG-PET images for the pre-specified voxel-wise analysis, and to define and estimate General Linear Models (GLM) yielding Statistical Parametric Maps (SPM) of each main effect. Pre-Processing includes format conversion, realignment, summing and co-registration to native MR space, tissue class segmentation, DARTEL registration and population template creation, normalization to standard template space and, smoothing of images.

Processed vMRI, ASL regional cerebral blood flow (rCBF) and F-FDG-PET images will be used to fit a GLM for statistical inference at every voxel in the brain. A design matrix for each main effect analysis specifies a statistical model to explain variance in the image space. Statistical models are implemented as two-sample t-tests for group analysis, and linear regression for continuous variables, with control

Sponsor:	TauRx Therapeutics Ltd.		
Protocol:	TRx-237-039		
Document Version No.:	3.0	Document Date:	07-JUN-2023

and nuisance variables in each case. For each main effect analysis, a design matrix is created to estimate beta weights explaining how each model vector independently influences variance in the processed images, plus some error. A contrast vector specifies the relative contribution of these model vectors, using standard least squares, and is associated with a t-statistic reflecting the combined weights divided by the standard error at each voxel. Multiple comparison's correction employing the familywise error rate (FWE) is used to control for the large number of t-tests being performed. The FWE threshold is set to  $p < .05$ .

Specifically, a whole-brain GLM analysis will be performed to derive voxel-wise statistical maps for each of the following main effects:

1. Delta Drug vs Delta control, vMRI
2. Delta Drug vs Delta control, 18F-FDG-PET
3. Delta Drug vs Delta control, ASL MRI

#### **5.11.1. VBM volumetric MRI analysis**

The voxel based morphometry (VBM) analysis will be performed using the approach described by John Ashburner ([www.fil.ion.ucl.ac.uk/~john/misc/VBMclass15.pdf](http://www.fil.ion.ucl.ac.uk/~john/misc/VBMclass15.pdf)), briefly described here:

##### Preprocessing

SPM → Spatial → Segment: To generate the roughly (via a rigid-body) aligned grey and white matter images of the subjects.

SPM → Tools → Dartel Tools → Run Dartel: (create Template): Determine the nonlinear deformations for warping all the grey and white matter images so that they match each other.

SPM → Tools → Dartel Tools → Normalise to MNI Space: Actually, generate the smoothed “modulated” warped grey and white matter images.

##### Statistical comparison

Within the SPM package we will construct a GLM for each voxel to compare the change in grey matter volume in the in the treated group with the change in grey matter volume in the control group. The comparison will be done correcting for the covariate total intracranial volume (TICV) and the randomization stratification variables. The effect of age and sex will also be tested.

Within the SPM package we will construct a GLM for each voxel to compare the change in white matter volume in the in the treated group with the change in white matter volume in the control group. The comparison will be done correcting for the same covariates mentioned above.

#### **5.11.2. FDG PET/CT analysis**

##### Preprocessing

Sponsor:	TauRx Therapeutics Ltd.		
Protocol:	TRx-237-039		
Document Version No.:	3.0	Document Date:	07-JUN-2023

---

As per the acquisition protocol the 6 by 5 minute reconstructed, attenuation corrected PET images will be realigned and summed to produce a single FDG image for each time point.

The single summed image will then be normalized into MNI space using the SPM provided template.

The normalized summed image will then be scaled using a ponds region of interest so that like for like comparisons can be made.

This step will be repeated using the cerebellum as the normalizing region of interest.

#### Statistical comparison

Within the SPM package we will construct a GLM for each voxel to compare the change in normalized pons scaled FDG uptake treated group with the change in FDG uptake in the control group. The comparison will be done correcting for randomization stratification variables as covariates, the effect of age and sex will be tested as well.

Within the SPM package we will construct a GLM for each voxel to compare the change in normalized cerebellum scaled FDG uptake treated group with the change in FDG uptake in the control group. The comparison will be done correcting for same covariates as mentioned above.

#### 5.11.3. ASL MR rCBF analysis

##### Preprocessing

The ASL rCBF images will be normalized into Montreal Neurological Institute (MNI) space using the SPM provided template.

##### Statistical comparison

Within the SPM package we will construct a GLM for each voxel to compare the change in normalized ASL rCBF images treated group with the change ASL rCBF in the control group. The comparison will be done correcting for same covariates as for the PET analysis.

#### 5.12. Safety Analyses

Safety analyses will be conducted using the Safety population. Key analyses will be repeated based on the Safetyv5 population. The analyses of the double-blind treatment phase are limited to the events up to the first dose of the open-label treatment phase. The eye exam is assigned to the double-blind treatment phase, if it was performed until the end of the Week 52 protocol-specified visit window.

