## 1.3. Study Protocol Versions

The following table shows an overview of the differences in duration, population, sample size and randomization ratios, and planned doses groups between the study protocol versions.

Sponsor:	TauRx Therapeutics Ltd.		
Protocol:	TRx-237-039		
Document Version No.:	3.0	Document Date:	07-JUN-2023

**Table 1** Protocol evolution

	Version 2.1	Version 3.0 – 4.1	Version ≥5.0
Duration of study	6 months (double-blind)	9 months (double-blind)	12 months (double-blind) + 12 months (open-label)
Population	Mild AD  (MMSE 20-25)	MCI-AD, or mild AD  (MMSE 20-27)  PET positive for amyloid	MCI-AD, mild AD, or moderate AD  (MMSE 16-27)  PET positive for amyloid
Target enrollment (randomization ratio according to doses below)	180  (1:1)	375  (2:2:1)	500 (≥v5.0: 450)  (1:4:4)
Planned doses (sample size)	HMTM 8 mg/day (N=90)  Placebo (N=90)	HMTM 8 mg/day (N=150)  Placebo (N=150)  HMTM 16 mg/day (N=75)	HMTM 8 mg/day (N=50)  Placebo/MTC (N=200)  HMTM 16 mg/day (N=200)

The primary efficacy analysis is performed based on the subjects randomized under protocol version 5.0 or higher, in which some MTC tablets were introduced to placebo treatment kits (on average twice per week spiking) as urinary discolorant to maintain the treatment blinding. In a sensitivity analysis, all randomized subjects are analyzed. Safety assessment will be performed based on all randomized subjects as well.

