#### 4.6. Control Group Labeling

With protocol version 5 on, drug supplies for the control group included tablets containing a urinary discolorant (MTC), 4 mg, dosed at an average frequency of two tablets per week (see Sections 1.3 and 2.1). This means, that most of the subjects randomized to placebo/control received at least one dose of MTC. The sponsor will provide an Excel file to Cytel, which will list the subjects who received placebo only and subjects who transitioned from placebo to MTC 8 mg/week. All other control group subjects will have received MTC 8 mg/week.

In the analysis, a few tables will present subjects who received placebo only separately from subjects who received at least one dose of MTC, which is then highlighted in the respective section of this SAP. In this case, the following treatment group labels will be used: "Placebo Only" and "MTC 8 mg/week".

For other analyses in which subjects randomized under a protocol version before version 5 are included (e.g., ITT population, see Section 3.1.1), the label for the control group will be "Placebo and/or MTC 8 mg/week", and for the analyses in which subjects randomized under a protocol version before version 5 are not included (e.g., ITTv5 population), the label for the control group will be "MTC 8 mg/week".

In the subject data listings control group subjects will be labeled as "Placebo Only" and "MTC 8 mg/week", respectively.

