#### 5.12.2. Adverse Events

Adverse events (AEs) will be coded using the MedDRA version 20.1 and are displayed in tables and listings using SOC and PT.

Treatment emergent AEs (TEAE) are defined as AEs with:

- Onset after first dose of study drug or
- Worsen in intensity after first dose of study drug or
- Worsen in treatment relationship after first dose of study drug

Based on the Safety population, a time-to-event analysis (event: any TEAE) will be performed using the model as described in Section 5.9.5). The time-to-first TEAE will be calculated as date of onset – date of first dose + 1, and subjects with no TEAE will be censored at the time of study discontinuation.

AEs are summarized by subject incidence rates, therefore, in any tabulation, a subject contributes only once to the count for a given AE (SOC or PT, most related occurrence, or most intense occurrence) regardless the number of episodes.

The total number of subjects and the numbers stratified by MedDRA SOC and PT, along with the corresponding percentage, with the following AE will be derived and summarized by treatment group and overall:

Sponsor:	TauRx Therapeutics Ltd.		
Protocol:	TRx-237-039		
Document Version No.:	3.0	Document Date:	07-JUN-2023

- Any TEAE (separate columns for true placebo and MTC)
- Any TEAE with an onset of Day 1 (separate columns for true placebo and MTC), complemented by a subject data listing
- Any TEAE (categorized by severity, and separate columns for true placebo and MTC), repeated for the Safetyv5 population.
- Any TEAE (categorized by severity) which occurred within two weeks after any COVID-19 vaccination (separate columns for true placebo and MTC)
- Any TEAEs assessed by the Investigator as related to treatment (i.e., related or possibly related) (separate columns for true placebo and MTC)
- Any TEAEs severe in intensity and assessed by the Investigator as related to treatment (as defined above) (separate columns for true placebo and MTC)
- Any TEAE that resulted in interruption or discontinuation of study drug (presented separately and combined) (separate columns for true placebo and MTC)
- Any SAE (separate columns for true placebo and MTC)
- Any serious adverse reaction (SAR), which are the SAEs judged to be possibly related or related to the study drug by the Investigator (separate columns for true placebo and MTC)
- Malignancies other than non-melanoma skin cancers (separate columns for true placebo and MTC)

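### Pooled double-blind safety tables give crude incidence across protocol versions of 6, 9 and 12 months, which biases Placebo Only downward against MTC and, less so, 8 mg against 16 mg

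*SAP*

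**What the plan says.** SAP Table 1 (Section 1.3) gives three planned durations: "6 months (double-blind" under version 2.1, "9 months (double-blind" under versions 3.0-4.1, and "12 months (double-blind) + 12 months (open-label" from version 5.0. Allocation of 8 mg : placebo : 16 mg went from 1:1 with no 16 mg arm, to 2:2:1, to 1:4:4. Of about 500 subjects, 450 are planned under version 5.0 or higher. The same section says: "Safety assessment will be performed based on all randomized subjects as well".

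Section 5.12 makes the Safety population the main set: "Safety analyses will be conducted using the Safety population. Key analyses will be repeated based on the Safetyv5 population". It does not define which analyses are key. Section 5.12.2 sets the measure: "AEs are summarized by subject incidence rates, therefore, in any tabulation, a subject contributes only once". Most AE tables there show true placebo and MTC in separate columns. Only two are marked for a Safetyv5 repeat: TEAEs by severity and the sponsor's AE Groupings.

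For the control split, Section 4.6 says that a sponsor file will "list the subjects who received placebo only and subjects who transitioned from placebo to MTC 8 mg/week". The MTC column holds anyone with at least one MTC dose. In version-5-restricted analyses the whole control group is labelled MTC.

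**The concern.** A crude proportion with an event depends on how long subjects were watched. Here planned follow-up differs by column, because the pre-version-5.0 subjects are spread unevenly. They weigh heavily in the small 8 mg arm ("HMTM 8 mg/day (N=50" under version 5.0 or higher), lightly in 16 mg, and make up the Placebo Only column.

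Placebo Only is also selected. A placebo subject who stays long enough to move to MTC leaves the column, and no rule assigns that subject's earlier time and events to placebo. SAP Section 6.3 points the same way: Placebo Only is a label only for subjects who do not enter the open-label phase.

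A reader comparing columns for a dose pattern, or for a difference between true placebo and the MTC-spiked control, would therefore see differences that come partly from observation time.

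**Working it through.** **Plan's own figures.** Arm size = N × ratio share. 180 at 1:1 gives 90/90. 375 at 2:2:1 gives 150/150/75. 450 at 1:4:4 gives 50/200/200. All match Table 1.

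**Inputs.** Pre-version-5.0 subjects: 500 − 450 = 50. Their split between version 2.1 and versions 3.0-4.1 is not given, so both extremes and the midpoint are shown. Assumed here: the same constant hazard in every column, no re-consent, no dropout, and a 12-month risk of 13%. That value is illustrative. Protocol Section 8.1.3.4 gives 13% for grouped anemia at 8 mg/day but no 52-week period.

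**Formula.** Risk by month t: p(t) = 1 − (1 − 0.13)^(t/12). So p(6) = 6.7%, p(9) = 9.9% and p(12) = 13.0%. Column incidence is the weighted mean.

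- All 50 under versions 3.0-4.1: 20 on 8 mg, 20 on placebo, 10 on 16 mg. 8 mg: (50 × 13.0 + 20 × 9.9)/70 = 12.1%. 16 mg: (200 × 13.0 + 10 × 9.9)/210 = 12.9%.
- All 50 under version 2.1: 25 on 8 mg, 25 on placebo, none on 16 mg. 8 mg: (50 × 13.0 + 25 × 6.7)/75 = 10.9%. 16 mg: 13.0%.

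| Pre-version-5.0 mix | 8 mg: n, mean months, % | 16 mg: n, mean months, % | Placebo Only: n, mean months, % | MTC: n, months, % |
|---|---|---|---|---|
| All 3.0-4.1 | 70, 11.1, 12.1 | 210, 11.9, 12.9 | 20, 9.0, 9.9 | 200, 12, 13.0 |
| Half and half | 72.5, 10.6, 11.5 | 205, 11.9, 12.9 | 22.5, 7.3, 8.1 | 200, 12, 13.0 |
| All 2.1 | 75, 10.0, 10.9 | 200, 12.0, 13.0 | 25, 6.0, 6.7 | 200, 12, 13.0 |

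**Artefact at 13%.**
- 16 mg minus 8 mg: 0.7-2.1 points (ratio 1.06-1.19), with a sampling SE of 4.3-4.5 points.
- MTC minus Placebo Only: 3.1-6.3 points (ratio 1.31-1.93), with an SE of 5.5-7.1 points.

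**Sensitivity.**
- Over true risks of 5-50%, the dose artefact is 0.3-6.9 points and the MTC artefact 1.2-20.7 points.
- If half of the pre-version-5.0 subjects extended to 12 months, the dose artefact at 13% falls to 0.4-1.0 points.
- Re-consent to version 5.0 or higher does not shrink the MTC artefact in the same way. A placebo subject who then takes MTC changes column, and those left behind still have 6-9 planned months.

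**After the change.** The yearly hazard is −ln(0.87) = 0.139. Subject-years to first event or end of period are p(t)/0.139 per subject, so the exposure-adjusted rate is 13.9 per 100 subject-years in every column. In Safetyv5 every arm has 12 planned months, so the dose artefact is zero.

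**The case against.** The strongest reply is that the plan already covers much of this.

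- Anemia is one of the AE Groupings, and both these and TEAEs by severity are repeated on Safetyv5. For those tables the dose artefact disappears. This stands.
- The primary comparison is barely touched. On the same assumptions the 16 mg/MTC incidence ratio is 0.99-1.00, and 1.01-1.06 with all control subjects pooled. This stands.
- SAP Section 6.1 describes earlier-version subjects who re-consented and completed 52 weeks, so the no-re-consent figures are upper ends for the dose comparison. This stands.
- The 13% is not a 52-week rate. The two AD studies with 8 mg/day arms ran 15 and 18 months. If it came from those, constant hazard gives 1 − 0.87^(12/15) = 10.5% or 1 − 0.87^(12/18) = 8.9% at 12 months. Early-onset events would also show less bias than a constant hazard implies.
- Exposure is tabulated before and after version 5.0, with true placebo and MTC apart, and there is a time-to-first-TEAE analysis. These help a reader notice the imbalance but do not adjust the AE tables. The time-to-event analysis covers any TEAE only, and the model section it refers to (5.9.5) compares 16 mg with control only.
- The key analyses may be listed more fully in the separate outputs document (SAP Section 13), which is not available here. In the SAP itself, no Safetyv5 repeat is named for SAEs, SARs, related TEAEs, discontinuations, malignancies, AESIs or PCS laboratory counts.

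A reader might infer that a false dose gradient and a false MTC excess will appear. The documents do not support that. They fix the direction of the bias, but not the version split, the extent of re-consent or the event timing. Nor do they say that the MTC spike will be judged harmless from these tables, and AE incidence is not formally tested.

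**Conclusion.** The pooled AE tables are biased in a known direction. Placebo Only is pushed down against MTC and, to a smaller degree, 8 mg against 16 mg. On the stated assumptions the size at a 13% risk is 3.1-6.3 points for Placebo Only and 0.7-2.1 points for dose.

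The dose part is minor: below its sampling error at that risk, smaller with re-consent, and already removed in two tables. Only at a 50% risk with all earlier subjects under version 2.1 does it reach its SE (6.9 against 6.7 points).

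The Placebo Only part remains. Safetyv5 cannot supply the comparison, and longer-followed subjects leave the column. A reader might also infer that the pooled Safety population is the wrong main set. It is the protocol-defined set (Protocol Section 17.3). Replacing it after unblinding would drop 20-25 of 70-75 subjects on 8 mg and the whole Placebo Only column, and the repair does not need it.

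**What to change.** 1. Keep the Safety population as the main set.
2. Beside crude incidence in the pooled AE and PCS tables, and in the Placebo Only/MTC split, add subjects with an event per 100 subject-years to first event or end of the double-blind phase. Show both measures, because an exposure-adjusted rate over-corrects for early-onset events.
3. In the split, assign time and events before the first MTC dose to placebo.
4. Name the SAE, SAR, related-TEAE, discontinuation, malignancy, AESI and PCS tables for Safetyv5 repetition, labelled as supportive.

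The cost is extra table programming with a population flag and a person-time denominator; dose dates are already in the eCRF. These analyses would be added after double-blind unblinding and should be labelled so. The Placebo Only/MTC split itself entered with SAP version 3.0, after partial unblinding. Exposure adjustment corrects follow-up only: the Placebo Only subjects were also enrolled under narrower MMSE criteria, so that comparison stays descriptive.
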